## SYNOPSIS

Title	A Randomized, Double Blind, Phase 2b Study to Evaluate the Effect of ORMD-0801 Compared to Placebo on Endogenous Glucose Production in Patients with Type 2 Diabetes Mellitus
Indication	Type 2 Diabetes Mellitus (T2DM)
Clinical Phase	Phase 2b
Study Treatment	ORMD-0801 (insulin)
Dose	ORMD-0801 8 mg Capsule
Dosage Regimen	BID
Formulation	Soft gel capsule [SBTI, disodium EDTA, fish oil, aerosol, and Tween 80], Recombinant Human Insulin
Mode of Administration	Oral
Primary Objective	

1. To assess the differences in endogenous glucose production in subjects with type 2 diabetes treated for 4 weeks either with ORMD-0801 or matching placebo following an intravenous infusion of [6,6-H2]-glucose tracer using AUC(0-last).

Secondary Objectives	

1. To compare the change from baseline in HbA1c levels measured at Week 4 in type 2 diabetic patients treated for 4 weeks with either ORMD-0801 or matching placebo.

2. To compare the change from baseline in plasma glucose levels measured at Week 4 in type 2 diabetic patients treated for 4 weeks with either ORMD-0801 or matching placebo.

3. To compare the change from baseline in ketone levels measured at Week 4 in type 2 diabetics treated for 4 weeks with either ORMD-0801 or matching placebo.

4. To compare the change from baseline in FFAs measured at Week 4 in type 2 diabetics treated for 4 weeks with either ORMD-0801 or matching placebo.

5. To compare the change from baseline in TC, LDLC, HDLC, and TG measured at Week 4 in type 2 diabetics treated for 4 weeks with either ORMD-0801 or matching placebo.

6. To assess the differences in endogenous glucose production in patients with type 2 diabetes treated for 4 weeks either with ORMD-0801 or matching placebo following an intravenous infusion of [6,6-H2]-glucose tracer using other parameters

	
including, but not limited to, <math>C_{max}</math>, <math>T_{max}</math>, <math>T_{lag}</math> and AUC over different time intervals.
 
7. To assess the safety of repeat administration of ORMD-0801 in patients with type 2 diabetes inadequately controlled on oral therapy.

Total Sample Size	Approximately 40 adult male and female subjects, aged 18 to 70 years, with T2DM.
Study Design	This study is designed to explore the efficacy of ORMD-0801 compared to placebo on endogenous glucose production in subjects with type 2 diabetes (T2DM). Subjects will undergo an initial Screening Visit (Visit 0) to establish their eligibility to participate in the study. At Visit 1 (2 weeks after the Screening Visit), qualifying subjects will be randomized to either ORMD-0801 (8 mg) or matching placebo, study medication will be dispensed and subjects will dose twice a day, once in the morning prior to breakfast and once at night prior to bedtime. Doses will occur at 45 minutes ( $\pm$ 15 minutes) before breakfast and no later than 10 AM each morning, and at 8 PM ( $\pm$ 120 minutes) each night, and no sooner than 1 hour after dinner. Subjects will return to the clinic, 2 weeks later, for Visit 2. At this visit, subject compliance will be assessed, medication will be dispensed, a blood sample will be collected to measure HbA1c and subjects will be questioned for any adverse events. Subjects will be scheduled to return to the clinic in 2 weeks for morning admission (8 AM $\pm$ 120 minutes) to the PK unit (Visit 3). Subjects will be provided with standardized meals and the morning dose in-clinic. A light standardized dinner meal will be provided at 6 PM $\pm$ 30 minutes. At approximately 8 PM ( $\pm$ 60 minutes, and no sooner than 1 hour after dinner), subjects will be dosed with their study medication and will be started on a 16-hour infusion of [6,6- $^2$ H 2 ]-glucose tracer. Blood samples will be collected to measure endogenous glucose (tracer attached), plasma glucose, metabolites and hormones for the duration of the infusion. Blood samples will be drawn at baseline (pre-infusion), 45, 90, 120 and 150 minutes, and 3, 4, 5, 6, 7, 8, 9, 10, 11, 12, 13, 14, 15 and 16 hours. Subjects will be required to remain fasting from the evening of Day 28 until the end of the infusion. Water intake will be unrestricted. On Day 29, blood sample will also be collected to measure HbA1c. Following completion of the infusion, the subjects will receive a standardized lunch and will be observed for an additional 6 hours. Prior to discharge, a physical examination will be performed, and blood/urine samples will be collected for safety chemistry, hematology and urinalysis, following which subjects will be discharged from the CRU and will exit the study.
Primary Endpoint	1. Difference in endogenous glucose production between active and placebo as measured by the glucose with tracer attached using AUC (0-16) as the primary parameter.

Secondary Endpoints	

1. Mean changes in HbA1c from baseline to Day 29 of the treatment period.

2. Mean changes plasma glucose levels from baseline to Day 29 of the treatment period.

3. Mean changes in ketones from baseline to Day 29 of the treatment period.

4. Mean Changes in FFA from baseline to Day 29 of the treatment period.

5. Mean change in TC, LDLC, HDLC and TG from baseline to Day 29 of the treatment period.

6a. Difference in endogenous glucose production between active and placebo as measured by the glucose with tracer attached using other parameters including, but not limited to:

a. AUC(0-2), AUC(0-4), AUC(0-8), AUC(0-12),

b. AUC(2-16), AUC(4-16), AUC(8-16), AUC(12-16),

c. Cmax,

d. Tmax, and

e. Tlag.

6b. Difference in metabolites (<math>\beta</math>-hydroxybutyrate, acetoacetate, lactate, pyruvate, FFA, glycerol) and hormones (insulin, C-peptide, glucagon) between active and placebo using the same AUC intervals as endogenous glucose production.

7. Safety assessed by adverse event reporting including adverse events of special significance such as hypoglycemia.

Duration of Participation	Subjects will be evaluated for participation in the study during a 1 to 3-week Screening period. Following Screening, eligible subjects will enter a 4-week double blind treatment period.
Subject Selection Criteria	Inclusion criteria 

1. Male and female subjects aged, 18 - 70 years.

2. Established diagnosis of T2DM for at least 6 months prior to Screening, with HbA1c <math>\geq 7.5\%</math>. and <math>\leq 11\%</math>.

3. Stable dose of metformin (at least 1500 mg or maximal tolerated dose) for a period of at least 3 months prior to Screening.

4. Taking metformin only or metformin in addition to no more than two of the following: DPP-4, SGLT-2, or TZD.

5. Body mass index (BMI) of up to 35 kg/m^2 at Screening and stable weight, with no more than 5 kg gain or loss in the 3 months prior to Screening.

6. Renal function – eGFR <math>> 30</math> ml/min/1.73 m^2.

7. Females of childbearing potential must have a negative serum pregnancy test result at Screening.

- a. Females who are not of childbearing potential are defined as:
  - i. Postmenopausal (defined as at least 12 months with no menses in women  $\geq$  45 years of age);
  - ii. Has had a hysterectomy and/or bilateral oophorectomy, bilateral salpingectomy, or bilateral tubal ligation/occlusion at least 6 weeks prior to screening; OR
  - iii. Has a congenital or acquired condition that prevents childbearing.
- b. Females of childbearing potential agree to avoid becoming pregnant while receiving study treatment and for 14 days after the last dose of study treatment by complying with one of the following:
  - i. Practice abstinence† from heterosexual activity; OR
  - ii. Use (or have her partner use) acceptable contraception during heterosexual activity. Acceptable methods of contraception are‡:
    1. Single method (one of the following is acceptable):
      - a. Non-hormonal intrauterine device (IUD);
      - b. vasectomy of a female subject's male partner.
    2. Combination method (requires use of two of the following):
      - a. diaphragm with spermicide (cannot be used in conjunction with cervical cap/spermicide);
      - b. cervical cap with spermicide (nulliparous women only);
      - c. contraceptive sponge (nulliparous women only);
      - d. male condom or female condom (cannot be used together).

†Abstinence (relative to heterosexual activity) can be used as the sole method of contraception if it is consistently employed as the subject's preferred and usual lifestyle and if considered acceptable by local regulatory agencies and ERCs/IRBs. Periodic abstinence (e.g., calendar, ovulation, sympto-thermal, post-ovulation methods, etc.) and withdrawal are not acceptable methods of contraception.

If a contraceptive method listed above is restricted by local regulations/guidelines, then it does not qualify as an acceptable method

	
of contraception for subjects participating at sites in this country/region.
 
Exclusion criteria
 

1. Subjects with insulin-dependent diabetes:

a. Has a history of type 1 diabetes mellitus or a history of ketoacidosis, or subject is assessed by the investigator as possibly having type 1 diabetes mellitus confirmed by a C-peptide < 0.7 ng/mL (0.23 nmol/L).

b. Has a history of other specific types of diabetes (e.g., genetic syndromes, secondary pancreatic diabetes, diabetes due to endocrinopathies, drug- or chemical-induced, and post-organ transplant).

2. Treatment with glucosidase inhibitor, insulin secretagogues (other than sulfonylureas), glucagon-like peptide 1 (GLP-1) agonists within 3 months prior to Visit 1.

3. History of any basal, pre-mix or prandial insulin (greater than 7 days) within 6 months prior to Screening.

4. History of > 2 episodes of severe hypoglycemia within 6 months prior to Screening.

5. History of hypoglycemic unawareness (episodes of severe hypoglycemia with seizure or requiring third party intervention or documented low blood glucose without associated autonomic symptoms).

6. Subjects with the following secondary complications of diabetes:

a. Active proliferative retinopathy as confirmed by a dilated ophthalmoscopy/retinal photography examination performed (by a qualified person as per the country legislation) within 6 months prior to Screening.

b. Renal dysfunction: estimated creatinine clearance < 30 ml/min.

c. History of proliferative retinopathy or severe form of neuropathy or cardiac autonomic neuropathy (CAN).

d. Uncontrolled or untreated severe hypertension defined as systolic blood pressure above or equal to 180 mmHg and/or diastolic blood pressure above or equal to 120 mmHg.

e. Presence of unstable angina or myocardial infarction within 6 months prior to Screening, Grade 3 or 4 congestive heart failure (CHF) according to the New York Heart Association (NYHA) criteria, valvular heart disease, cardiac arrhythmia requiring treatment, pulmonary hypertension, cardiac surgery, history/occurrence of coronary angioplasty and/or stroke or transient ischemic attack (TIA) within 6 months prior to Screening.

--	------------------------------------------------------------------------------------------------------------------------------------------------------------------------------------------------------------------------------------------------------------------------------------------------------------------------------------------------------------------------------------------------------------------------------------------------------------------------------------------------------------------------------------------------------------------------------------------------------------------------------------------------------------------------------------------------------------------------------------------------------------------------------------------------------------------------------------------------------------------------------------------------------------------------------------------------------------------------------------------------------------------------------------------------------------------------------------------------------------------------------------------------------------------------------------------------------------------------------------------------------------------------------------------------------------------------------------------------------------------------------------------------------------------------------------------------------------------------------------------------------------------------------------------------------------------------------------------------------------------------------------------------------------------------------------------------------------------------------------------------------------------------------------------------------------------------------------------------------------------------------------------------------------------------------------------------------------------------------------------------------------------------------------------------------------------------------------------------------------------------------------------------------------------------------------------------------------------------------------------------------------------------------------------------------------------------------------------------------------------------------------------------------------------------------------------------------------------------------------------------------------------

	

7. Subjects with psychiatric disorders which, per investigator judgment, may have impact on the safety of the subject or interfere with subject's participation or compliance in the study.

8. Subjects who needed (in the last 12 months) or may require systemic (oral, intravenous, intramuscular) glucocorticoid therapy for more than 2 weeks during the study period.

9. Laboratory abnormalities at Screening including:

a. C-peptide < 0.7 ng/mL (0.23 nmol/L).

b. Abnormal serum thyrotropin (TSH) levels below the lower limit of normal or > 1.5X the upper limit of normal.

c. Elevated liver enzymes (alanine transaminase (ALT), alanine aminotransferase (AST), alkaline phosphatase) > 2X the upper limit of normal.

d. Very high triglyceride levels (> 600 mg/dL); a single repeat test is allowable.

e. Any relevant abnormality that would interfere with the efficacy or the safety assessments during study treatment administration.

10. Positive history of active liver disease (other than non-alcoholic hepatic steatosis), including chronic hepatitis B or C, primary biliary cirrhosis, or active symptomatic gallbladder disease.

11. Positive history of HIV.

12. Use of the following medications:

a. History of any basal, pre-mix or prandial insulin (greater than 7 days) within 6 months prior to Screening.

b. Administration of thyroid preparations or thyroxine (except in subjects on stable replacement therapy) within 6 weeks prior to Screening.

c. Administration of systemic long-acting corticosteroids within two months or prolonged use (more than one week) of other systemic corticosteroids or inhaled corticosteroids (if daily dosage is > 1,000 µg equivalent beclomethasone) within 30 days prior to Screening. Intra-articular and/or topical corticosteroids are not considered systemic.

d. Use of medications known to modify glucose metabolism or to decrease the ability to recover from hypoglycemia such as oral, parenteral, and inhaled steroids (as discussed above), and immunosuppressive or immunomodulating agents.

13. Known allergy to soy.

14. Subject is on a weight loss program and is not in the maintenance phase, or subject has started weight loss medication (e.g., orlistat or liraglutide), within 8 weeks prior to Screening.

--	-------------------------------------------------------------------------------------------------------------------------------------------------------------------------------------------------------------------------------------------------------------------------------------------------------------------------------------------------------------------------------------------------------------------------------------------------------------------------------------------------------------------------------------------------------------------------------------------------------------------------------------------------------------------------------------------------------------------------------------------------------------------------------------------------------------------------------------------------------------------------------------------------------------------------------------------------------------------------------------------------------------------------------------------------------------------------------------------------------------------------------------------------------------------------------------------------------------------------------------------------------------------------------------------------------------------------------------------------------------------------------------------------------------------------------------------------------------------------------------------------------------------------------------------------------------------------------------------------------------------------------------------------------------------------------------------------------------------------------------------------------------------------------------------------------------------------------------------------------------------------------------------------------------------------------------------------------------------------------------------------------------------------------------------------------------------------------------------------------------------------------------------------------------------------------------------------------------------------------------------------------------------------------------------------------------------------------------------------------------------------------------------------------------------------------------------------------------------------------------------------------------------------------------------------------------------------------------------------------

## LIST OF ABBREVIATIONS AND DEFINITIONS OF TERMS

AE	adverse event
ALT	alanine aminotransferase
AST	aspartate aminotransferase
AUC	area under the curve
BID	twice a day
BUN	blood urea nitrogen
CAN	cardiac autonomic neuropathy
CFR	Code of Federal Regulations
CHF	congestive heart failure
C max	maximum concentration
CRO	contract research organization
CRU	clinical research unit
CTCAE	Common Terminology Criteria for Adverse Events
DBP	diastolic blood pressure
DPP-4	dipeptidyl peptidase 4
ECG	electrocardiogram
eCRF	electronic case report form
eGFR	estimated glomerular filtration rate
EDC	electronic data capture
EDTA	ethylenediaminetetraacetic acid
ET	early term
EW	early withdrawal
FDA	Food and Drug Administration
FFA	free fatty acid
GCP	Good Clinical Practice
GGT	gamma-glutamyltransferase
GLP-1	glucagon-like peptide 1
HbA1c	hemoglobin A1c
HDLC	high-density lipoprotein cholesterol
HIPAA	Health Insurance Portability and Accountability Act of 1996
HIV	Human Immunodeficiency Virus
IB	Investigator's Brochure
ICF	informed consent form
ICH	International Council for Harmonisation
IND	Investigational New Drug application
IRB	Institutional Review Board
IUD	intrauterine device
LDLC	low-density lipoprotein cholesterol
MedDRA	Medical Dictionary for Regulatory Activities
NYHA	New York Heart Association
PK	pharmacokinetic
SAE	serious adverse event
SBP	systolic blood pressure
SBTI	soybean trypsin inhibitor

SGLT-2	sodium-glucose co-transporter 2
SOP	standard operating procedure
TC	total cholesterol
TG	triglycerides
TEAE	treatment-emergent adverse event
T max	time to reach maximum concentration
TIA	transient ischemic attack
T lag	absorption lag time
TSH	serum thyrotropin
TZD	thiazolidinedione
T2DM	type 2 diabetes mellitus
WCBP	woman of childbearing potential
WHO	World Health Organization

## 1 INTRODUCTION

Endogenous insulin – secreted by the  $\beta$ -cells of the endocrine pancreas – flows to the liver in the portal blood before reaching the systemic circulation through the hepatic veins. Following oral administration, the insulin in ORMD-0801 is absorbed through the gastrointestinal mucosa into the mesenteric veins (mostly, the superior mesenteric vein that drains blood from the jejunum and ileum) and reaches the liver *via* the portal vein, thereby mimicking the route of entry of endogenous insulin. The main action of insulin in the liver is to suppress glucose production; for this action, sensitivity is higher, and onset and offset time of this action are faster than for insulin stimulation of glucose uptake by peripheral tissues. First-pass extraction of insulin by the liver is 50-60%; recirculation raises this percentage to ~80%. As a consequence, portal plasma insulin concentrations normally are ~3-fold higher than peripheral insulin levels.

The hypothesis behind ORMD-0801 is that sufficient oral insulin survives gastrointestinal degradation to arrive at the liver where it inhibits glucose production and, through this effect, lowers fasting plasma glucose concentrations. As the majority of this exogenous insulin dose is degraded in the liver, the resulting systemic insulin levels may be only marginally increased, thereby avoiding the risk of hypoglycemia.

The use of glucose tracers is the standard non-invasive approach to measure endogenous glucose production (EGP). A tracer (in this protocol, [6,6-H2]-glucose, a stable isotope of glucose) infused intravenously at a constant rate will equilibrate with endogenous glucose across its distribution space within ~3 hours. From this time onward, the ratio of the tracer infusion rate to the plasma tracer/tracee ratio (as assayed by GCMS) measures EGP. As compared to placebo, oral insulin is expected to reduce EGP over the ensuing 13 hours of continued fasting. In patients with type 2 diabetes, EGP is known to be abnormally elevated and to contribute the hyperglycemia. Oral insulin is therefore addressing a key pathophysiological derangement of type 2 diabetes.

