
### 3 INVESTIGATIONAL PLAN

#### 3.1 Overall Study Design and Plan

This study is designed to explore the efficacy of ORMD-0801 compared to placebo on endogenous glucose production in subjects with type 2 diabetes (T2DM). Subjects will undergo an initial Screening Visit (Visit 0) to establish their eligibility to participate in the study. At Visit 1 (2 weeks after the Screening Visit), qualifying subjects will be randomized to either ORMD-0801 (8 mg) or matching placebo, study medication will be dispensed and subjects will dose, twice a day, once in the morning prior to breakfast and once at night prior to bedtime. Doses will occur at 45 minutes ( $\pm$  15 minutes) before breakfast and no later than 10 AM each morning, and at 8 PM ( $\pm$  120 minutes) each night, and no sooner than 1 hour after dinner. Subjects will return to the clinic, 2 weeks later, for Visit 2. At this visit, subject compliance will be assessed, medication will be dispensed, a blood sample will be collected to measure HbA1c and subjects will be questioned for any adverse events. Subjects will be scheduled to return to the clinic in 2 weeks for morning admission (8 AM  $\pm$  120 minutes) to the PK unit (Visit 3). Subjects will be provided with standardized meals and the morning dose in-clinic. A light standardized dinner meal will be provided at 6 PM  $\pm$  30 minutes. At approximately 8 PM ( $\pm$  60 minutes, and no sooner than 1 hour after dinner), subjects will be dosed with their study medication and will be started on a 16-hour infusion of [6,6-H2]-glucose tracer. Blood samples will be collected to measure endogenous glucose (tracer attached), plasma glucose, metabolites and hormones for the duration of the infusion. Blood samples will be drawn at baseline (pre-infusion), 45, 90, 120 and 150 minutes, and 3, 4, 5, 6, 7, 8, 9, 10, 11, 12, 13, 14, 15 and 16 hours (see [Table 2](#) for blood draw schedule). Subjects will be required to remain fasting from the evening of Day 28 until the end of the infusion. Water intake will be unrestricted. On Day 29, blood sample will also be collected to measure HbA1c. Following completion of the infusion, the subjects will receive a standardized lunch and will be observed for an additional 6 hours. Prior to discharge, a physical examination will be performed, and blood/urine samples will be collected for safety chemistry, hematology and urinalysis, following which subjects will be discharged from the CRU and will exit the study.

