**Table 1: Schedule of Events from Screening (Visit 0) to Discharge/End of Study (Visit 3, Day 29).**

	Screening	Treatment Period			Discharge / End of Study	Early Withdrawal
				TRACER Infusion		
Visit	0	1	2	3		
Week	-3 to -1	0	2		4	
Day	-21 to -7	0	14	28	29	
Informed Consent	X					
Inclusion/Exclusion	X	X				
Demographics (sex, age, race and ethnicity)	X					
Medical and Social History (including tobacco, alcohol, caffeine and drug use)	X					
Prior/Concomitant Medications	X	X	X	X	X	X
Physical Examination	X				X	X
12-lead ECG	X					
Height, Weight, BMI	X	X	X	X		X
Vital Signs	X	X	X	X	X	X
Chemistry, Hematology, Urinalysis	X				X 	X
Blood Collection for Plasma Glucose, Metabolites and Hormones	X			X	X	
Urine Drug Screen	X					
Serum Pregnancy Test	X					
Urine Pregnancy Test				X		
Breathalyzer	X	X	X	X	X	

	Screening	Treatment Period			Discharge / End of Study	Early Withdrawal
				TRACER Infusion		
Visit	0	1	2		3	
Week	-3 to -1	0	2		4	
Day	-21 to -7	0	14	28	29	
HbA1c	X	X	X	X	X	
Randomization		X				
Dispense study medication		X	X			
Collect study medication and review for compliance			X	X		
CRU Admission				X		
In-Clinic Dosing				X		
TRACER Infusion				X	X	
Blood Collection for Tracer Marked Glucose, Metabolites and Hormones				X	X	
Standard Meals				X	X	
CRU Discharge					X 	X
Adverse Events		X	X	X	X	X
End of Study					X	X

 Weight will be measured at each visit. Height will be measured and BMI will be calculated at Screening.

 Blood draw will be performed after the 16-hour infusion is complete.

 A blood plasma sample will be collected at Screening and during infusion for assessment of plasma glucose, metabolites and hormones according to [Table 2](#).

 Serum pregnancy test and urine pregnancy test will be performed for women of childbearing potential (WCBP) only.

 Subjects will be started on a 16-hour infusion of TRACER immediately following dosing. Refer to [Appendix A](#) (Guidelines for TRACER Infusion).

 Blood samples will be collected during the duration of infusion based on the blood draw schedule in [Table 2](#).

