## 14 APPENDIX A

### 14.1 Guidelines for TRACER Infusion

#### EGP Protocol

**Tracer:** [6,6-H2]-glucose (from Cambridge Isotope Laboratories

[<https://shop.isotope.com/productdetails.aspx?itemno=DLM-349-PK>])

**Constant tracer infusion rate:**  $0.28 \text{ } \mu\text{mol} \cdot \text{min}^{-1} \cdot \text{kg}^{-1}$  ( $= 51 \text{ } \mu\text{g} \cdot \text{min}^{-1} \cdot \text{kg}^{-1}$ ) via an indwelling catheter in an antecubital vein. Assuming participants have dinner at 18:00pm, the tracer infusion can start at 20:00pm and continue until 12 noon the following day, *i.e.*, for 960 min.

**Example:** In a T2D subject weighing 90 kg, the total amount of tracer would be  $0.28 \times 960 \times 90 = 24,192 \text{ } \mu\text{mol}$  ( $= 4.41 \text{ g}$  per study). Rounding this up, one dissolves 4.5 g of [6,6-H2]-glucose in 500 mL of saline: this is the mother solution (from which a 5 mL aliquot must be saved together with the plasma samples) to be given at a rate of 0.5 mL/min to the 90-kg person for 960 min.

**Blood sampling:** through a cannula in a contralateral antecubital vein, one sample is taken prior to starting the tracer infusion, then blood is drawn every hour till the end.

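### The only EGP formula in the protocol needs a flat tracer ratio, but the infusion is unprimed, starts with the dose, and the primary AUC counts the hours before equilibration

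*Combined protocol and SAP*

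**What the plan says.** Section 1 (Introduction) says that tracer "infused intravenously at a constant rate will equilibrate with endogenous glucose across its distribution space within ~3 hours", and that from then on "the ratio of the tracer infusion rate to the plasma tracer/tracee ratio (as assayed by GCMS) measures EGP". It expects that "oral insulin is expected to reduce EGP over the ensuing 13 hours of continued fasting", and that lower production will in turn lower fasting plasma glucose.

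Appendix A (Guidelines for TRACER Infusion) gives a "Constant tracer infusion rate" of 0.28 µmol/min/kg for 960 min and mentions no priming dose. The footnotes to Table 1 fix the start: "Subjects will be started on a 16-hour infusion of TRACER immediately following dosing".

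Sections 2 and 8.3 make AUC(0-16) the primary parameter and describe it as glucose carrying the tracer. Sections 6.2.1 and 8.4.1 add further windows, some early (0-2, 0-4) and some late (8-16, 12-16). None of these sections says how EGP is obtained from the assay results. Section 8 leaves further detail to a statistical analysis plan.

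On sampling, section 3.1 says: "Blood samples will be collected to measure endogenous glucose (tracer attached), plasma glucose, metabolites and hormones for the duration of the infusion". Table 2 lists 19 times, each with both a tracer and a glucose tube.

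**The concern.** The rate/ratio formula is a steady-state identity, and two features of this design keep TTR moving. An unprimed infusion has to build up to plateau, and a drug that lowers EGP moves the plateau itself. While TTR moves, the formula carries an error proportional to the size of the glucose pool. The drug is meant to change that pool, so the error need not be equal in the two arms and randomization does not remove it. Each subject has one infusion and no baseline infusion, so it cannot be subtracted either.

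The primary window adds a conflict within the protocol. The Introduction says the formula becomes valid at about 3 h, while the primary AUC starts at 0 h. What is at stake is the size of the primary treatment difference and, in some scenarios, whether a small difference is real.

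**Working it through.** **1. The protocol's own figure.** Appendix A's example begins "In a T2D subject weighing 90 kg, the total amount of tracer would be" and continues 0.28 × 960 × 90 = 24,192 µmol. At 182.17 g/mol this is 4.41 g, and 0.28 × 182.17 = 51.0 µg/min/kg. Both figures reproduce. The constant infusion uses the whole 24,192 µmol, so the budget contains no prime.

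**2. Mass balance (one pool).** Let F be the infusion rate, V the distribution volume and G plasma glucose.

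- dTTR/dt = (F − TTR × EGP) / (V × G)
- Rearranged: F/TTR = EGP + V × G × d(ln TTR)/dt

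The second term is the error. It is zero only when TTR is flat, and it scales with G.

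**3. Build-up.** With constant EGP, TTR as a fraction of plateau is 1 − exp(−kt), where k = EGP/(V × G). The documents give no EGP, glucose or volume values. I assume EGP 12 µmol/kg/min, G 9–11 mmol/L and V 0.13–0.25 L/kg.

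| | V 0.13, G 9 | V 0.25, G 11 |
|---|---|---|
| Pool V × G (µmol/kg) | 1,170 | 2,750 |
| k (per min) | 12/1,170 = 0.01026 | 12/2,750 = 0.00436 |
| TTR at 180 min, share of plateau | 1 − e^−1.846 = 84% | 1 − e^−0.785 = 54% |
| Time to 95% of plateau, ln(20)/k | 292 min = 4.9 h | 686 min = 11.4 h |

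At t = 0, TTR is zero, so F/TTR has no value and AUC(0-16) cannot be formed from it.

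**4. Effect on the AUC, 3–16 h.** On placebo F/TTR = EGP/(1 − e^−kt). Its mean over 180–960 min, relative to EGP, is ln[(e^960k − 1)/(e^180k − 1)]/(780k). This is about 1.02 and 1.17 for the two columns. The trapezoidal rule at the Table 2 times gives an overstatement of 2–18%. Solving step 2 numerically for an active arm at constant glucose gives:

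| Scenario on active | F/TTR result |
|---|---|
| 20% suppression from 3 h onward | 70–86% of the true difference |
| 20% suppression over 0–6 h | 138–141% of the true 3–16 h difference; 69–70% of the true 0–16 h difference |
| EGP 20% lower throughout, same glucose | shows 14–19% |
| EGP 20% lower throughout, glucose 20% lower | shows exactly 20%, because k is unchanged |
| Same EGP, glucose 1–2 mmol/L lower | false reduction of 0.7–5.1% |

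**5. Wider assumptions.** Take EGP 10–18, G 8–14, V 0.13–0.25, with glucose responding when EGP is stepped down. TTR at 3 h is then 40–96% of plateau. The ratio of apparent to true difference runs from 0.70 to 2.01 across suppression patterns and start times (45 min or 3 h). It is 0.97–1.01 for a suppression confined to 4–10 h.

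**6. With the correction.** Steele form: EGP = [F − V × G × dTTR/dt]/TTR, taken between adjacent samples. For the suppression from 3 h (step 4 assumptions), recovery is about 100% with V right. It is roughly 89–109% with V wrong by 30%, depending on how the slope is taken from the samples. Under the wider assumptions with V wrong by 25%, recovery over 3–16 h is 0.98–1.02 for a sustained 20% suppression from 1 h, but 0.75–1.26 for one confined to 1–6 h.

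**The case against.** Four points on the other side have force.

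- **The formula sits in the Introduction.** A reader might infer that the trial will compute its primary endpoint as F/TTR. The documents do not establish that. The analysis sections give no formula, and section 8 defers detail to an analysis plan whose EGP calculation is not in the text available. What stands is that F/TTR is the only calculation stated and no alternative is prespecified.
- **Direction.** A reader might infer a bias toward the drug, because a smaller glucose pool reaches plateau sooner. That case needs glucose to fall with EGP unchanged. The protocol's mechanism is the reverse: production falls and glucose follows. If both fall in proportion, the relative effect is unbiased. If EGP is lower throughout and glucose does not move, the error works against the drug.
- **Late windows are already listed.** AUC(8-16) and AUC(12-16) are secondary parameters, and over 8–16 h F/TTR overstates the placebo AUC by only 0.2–5.6% under the step 4 assumptions. They give a partial check, but they do not repair the primary parameter.
- **The correction is not free.** It needs an assumed V and a TTR slope taken from discrete assays. That adds noise, which cannot be sized from the documents. For an early, brief suppression it remains sensitive to V.

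**Conclusion.** The concern holds as a gap in the definition of the primary endpoint and should be corrected. Three things follow from the documents without any assumption: the only stated formula requires a flat TTR; the infusion described is unprimed and starts with the dose; and AUC(0-16) includes hours that the Introduction itself places before equilibration.

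The size rests on assumed EGP, glucose and volume. In the narrower set, TTR at 3 h is 54–84% of plateau, and the treatment difference over 3–16 h can be read at anything from 70% to about 140% of its true value. The wider set extends the upper end to about twice the true value, and for late, self-contained suppression the error nearly vanishes. No effect on power can be given, because the protocol states no SD, effect size or alpha.

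**What to change.** In the analysis plan, before unblinding:

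1. Define EGP between adjacent samples with the Steele non-steady-state equation, using the paired glucose and TTR values. State V and repeat the primary analysis with V varied by ±30%.
2. Start the primary EGP AUC no earlier than the protocol's own equilibration time, for example AUC(3-16). Label EGP results from earlier windows as exploratory.
3. Report F/TTR as a sensitivity analysis over AUC(8-16) and AUC(12-16), with a prespecified check by arm that TTR is flat there.
4. Take F from the assayed infusate and the recorded pump rate. Appendix A's example solution, 4.5 g in 500 mL, is "to be given at a rate of 0.5 mL/min to the 90-kg person for 960 min". That delivers 4.5/500 × 0.5/90 = 50.0 µg/min/kg, about 2% below the stated 51, and the two figures should be reconciled.
5. Reconcile Appendix A's hourly sampling with the 45, 90, 120 and 150 min draws in Table 2.

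The cost is text and programming, with no new visits or blood draws. The drawbacks are an assumed pool volume, some noise from the TTR slope, and a primary window that no longer counts drug effect in the first 3 h.
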